## Appendix I – Karnofsky Performance Status Scale

Percentage	
100	Normal, no complaints, no evidence of disease
90	Able to carry on normal activity; minor signs or symptoms of disease
80	Normal activity with effort; some signs or symptoms of disease
70	Cares for self; unable to carry on normal activity or do active work
60	Requires occasional assistance, but is able to care for most of his/her needs
50	Requires considerable assistance and frequent medical care
40	Disabled; requires special care and assistance
30	Severely disabled, hospitalization indicated. Death not imminent
20	Very sick, hospitalization necessary, active supportive treatment necessary
10	Moribund, fatal processes, progressing rapidly
0	Dead

## Appendix II — GVHD Grading Scales

### Acute GVHD:

Consensus Clinical Stage and Grade of Acute GVHD (Glucksberg *et al*, 1974; Thomas *et al*, 1975, Przepiorka *et al*, 1995)

Stage	Skin	Liver	Lower Gastrointestinal Tract	Upper Gastrointestinal Tract
1	Maculopapular rash <25% of body surface	Bilirubin 2.0 – 3.0 mg/dl	Diarrhea 500 – 1000 mL/day or 280 – 555 mL/m 	No protracted nausea and vomiting
2	Maculopapular rash 25- 50% body surface	Bilirubin 3.1 – 6.0 mg/dl	Diarrhea 1000 – 1500 mL/day or 556 – 833 mL/m 	Persistent nausea, vomiting or anorexia
3	Generalized erythroderma	Bilirubin 6.1 – 15.0 mg/dl	Diarrhea >1500 mL/day or >833 mL/m 	
4	Generalized erythroderma with bullous formation and desquamation	Bilirubin > 15 mg/dl	Severe abdominal pain, with or without ileus, or stool with frank blood or melena	

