#### **Exclusion Criteria (on or before Day 1 of Cycles 2-4)**

Patients must meet the following criteria at the time of screening for the next cycle unless otherwise noted.

- 8.5.5** Active uncontrolled infection. An active uncontrolled infection is defined as hemodynamic instability attributable to sepsis or new symptoms, worsening physical signs or radiographic findings attributable to infection. Persisting fever without signs or symptoms will not be interpreted as an active uncontrolled infection. Subjects with a controlled infection receiving definitive therapy for 72 hours prior to screening are eligible.
- 8.5.6** Any new GVHD except grade I acute GVHD during the most recent cycle.
- 8.5.7** Any form of iatrogenic immunosuppression except  $< 0.5 \text{ mg/kg/day}$  of prednisone or equivalent.
- 8.5.8** Unresolved veno-occlusive disease of the liver, defined as persistent bilirubin abnormalities not attributable to GVHD and ongoing organ dysfunction (renal, ascites).
- 8.5.9** Subjects who are pregnant, breast feeding or sexually active and unwilling to use effective birth control for the remaining duration of the study.
- 8.5.10** Radiation therapy during the most recent cycle.

- 8.5.11** Disease progression during the most recent cycle.
- 8.5.12** Exposure to any other investigational agent, device or procedure during the most recent cycle.
- 8.5.13** Patients or donors with any medical or psychological condition that, in the opinion of the Investigator, might interfere with the subject's continuation in the trial, pose any additional risk for the patient/donor, or confounds the assessments of the subject.
- 8.5.14** Any condition resulting in prolongation of the most recent cycle beyond 8 weeks. If in the view of the investigator, postponing the next cycle is justified for any reason, this is allowed as long as the current cycle does not exceed 8 weeks. If longer than 8 weeks, patients will not receive further therapy on study.
- 8.5.15** Consent withdrawal by patient

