### **14.2 Secondary Endpoints**

Secondary endpoints of safety and efficacy are measured as below.

- OS at 12 months
- Cumulative incidence of grade II-IV acute graft-versus-host disease (aGVHD II-IV) at 3 months
- PFS at 6 and 12 months in patients
- Cumulative incidence of relapse at 6 and 12 months
- Complete remission (CR) at 6 and 12 months
- Cumulative incidence of non-relapse mortality (NRM) at 6 and 12 months
- Best response until next line of treatment, death, or last follow up, whichever occurs sooner

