### University Of Minnesota Acute GVHD Grading

Acute GVHD Grade	Skin Stage	Liver Stage	Lower GI Stage	Upper GI Stage
I	1-2	0	0	0
II	3	1	1	1
III	-	2-4	2-3	
IV	4	-	4	

- Each column identifies minimum criteria for organ grade.
- Each grade is based on maximum stage for each individual organ involved

e.g. Grade II = skin stage 3 and/or liver stage 1 and/or gut stage 1 and/or UGI stage 1

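### The two acute GVHD tables in Appendix II do not fit together for the upper GI tract, so the grade I/II boundary is left to site practice

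*Combined protocol and SAP*

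**What the plan says.** The Appendix II staging table has rows for stages 1 to 4. In the upper-GI column only two are filled: stage 1 is "No protracted nausea and vomiting" and stage 2 is "Persistent nausea, vomiting or anorexia". There is no stage 0 row.

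The University of Minnesota grading table that follows lists upper-GI stage 0 under grade I and upper-GI stage 1 under grade II, with nothing under grades III and IV. Its notes say "Each column identifies minimum criteria for organ grade" and "Each grade is based on maximum stage for each individual organ involved". The worked example repeats the mapping in running text: "Grade II = skin stage 3 and/or liver stage 1 and/or gut stage 1 and/or UGI stage 1".

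The resulting grade is used in two places that matter here:

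- Section 14.2 lists as a secondary endpoint "Cumulative incidence of grade II-IV acute graft-versus-host disease (aGVHD II-IV) at 3 months".
- Section 8.5.6 excludes from the next cycle a patient with "Any new GVHD except grade I acute GVHD during the most recent cycle". The opening paragraph of Section 8.5 says the same, and Section 8.8 lists it among the possible reasons for ending study treatment.

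**The concern.** The staging table works with upper-GI levels 1 and 2; the grading table works with levels 0 and 1. The only level they share is stage 1. The first table words it as the lack of a protracted symptom, and the second treats it as sufficient for grade II. The level needed for grade I is defined nowhere.

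A grader can read stage 1 in two ways. Either it covers patients without upper-GI symptoms, or it covers patients whose symptoms are present but not protracted. Under either reading, a patient with mild skin involvement only, or with brief nausea, can be moved to grade II by the upper-GI column.

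The trial is multi-center, and Appendix II is the only acute GVHD grading scale in the documents, so sites have no other text in the plan to settle the conflict. Two sites could grade the same patient differently. At one the patient would count as a II-IV event and be barred from the next cycle; at the other, neither.

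**Working it through.** The documents give no expected II-IV rate, power or threshold that depends on this definition, so there is no planned figure to reproduce. The check is of the tables themselves.

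**Step 1. Code the grading table.** The overall grade is the highest grade reached by any organ.

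| Organ | Stage and the grade it gives |
|---|---|
| Skin | 1-2 gives I; 3 gives II; 4 gives IV |
| Liver | 1 gives II; 2-4 gives III |
| Lower GI | 1 gives II; 2-3 gives III; 4 gives IV |
| Upper GI | 0 gives no more than I; 1 or above gives II (listed stages are minimums) |

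**Step 2. Score the stage 1 description two ways.** Take all 5 x 5 x 5 = 125 combinations of skin, liver and lower-GI stage (0 to 4 each). Grade each with the upper-GI entry set to stage 1, as the staging table words it, and then to stage 0. Setting it to 0 is a comparison only, not a proposed rule.

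| Skin stage (liver 0, lower GI 0) | Upper-GI entry scored 0 | Upper-GI entry scored 1 |
|---|---|---|
| 0 | 0 | II |
| 1 | I | II |
| 2 | I | II |
| 3 | II | II |
| 4 | IV | IV |

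These first three rows are the only combinations of the 125 that cross into grade II; any liver or lower-GI involvement is already grade II or higher. None of the 125 changes its grade III-IV status.

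**Step 3. Direction.** Because the grade is a maximum over organs, scoring 1 instead of 0 can never lower it. Misgrading from this source can only add II-IV events.

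**Step 4. Size per patient.** With the 32 evaluable patients of Section 15.1, one patient who would not otherwise be II-IV adds 1/32 = 3.1 points. This treats the 3-month cumulative incidence as a simple proportion, which is exact when no one is censored before 3 months.

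**Step 5. Total size, under assumptions only.** Let t be the true II-IV rate and m the share of the remaining patients who are misgraded. The observed rate is t + (1 - t)m, and the extra events are 32(1 - t)m. Neither t nor m is in the documents. For assumed t of 20-40% and m of 5-25%:

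- lowest observed rate: 0.20 + 0.80 x 0.05 = 24%
- highest observed rate: 0.40 + 0.60 x 0.25 = 55%
- fewest extra events: 32 x 0.60 x 0.05 = 1.0
- most extra events: 32 x 0.80 x 0.25 = 6.4

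The width of this range shows that the total cannot be fixed from the plan.

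**Step 6. Stopping rule.** Section 15.4 counts only grade III-IV events, and the upper-GI column leads to neither grade. The exact stopping probabilities of its boundary are 4.9% at a true rate of 10% and 86.1% at 30%, in line with the stated limit of 5% and the stated 86%. They do not depend on this point.

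**The case against.** The strongest reply is that no experienced grader would read the table literally. The notes refer to organs that are involved, and grade I lists upper-GI stage 0, so an uninvolved upper GI tract is evidently meant to be stage 0. This stands in part. It defeats the extreme inference a reader might draw, that grade I can never be reached and every patient becomes grade II, because that requires staging an organ that is not involved. It does not settle brief, non-protracted symptoms, and it relies on a stage the plan never defines.

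Three further limits are accepted:

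- A reader might infer that persistent nausea has no grade, since stage 2 is absent from the grading table. The note that listed stages are minimums places it at grade II or above.
- A reader might size the effect from Section 9.2, which lists nausea as very common (10% or more) with decitabine: 0.10 x 32 = 3.2 patients, or 10 points. The documents do not support this. No section says drug-related nausea is to be scored as GVHD, and the sum ignores patients already at grade II-IV. Even granting full misattribution, an assumed true rate of 20-40% and independence, it falls to 3.2 x 0.80 = 2.6 or 3.2 x 0.60 = 1.9 patients, that is 8 or 6 points.
- The affected endpoint is secondary, and Section 15.2 makes its analysis mainly descriptive.

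A displaced cell in the staging table cannot be fully excluded. However, the other columns line up with their stages, and a one-row shift would need a stage 0 row that the table does not have.

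**Conclusion.** The point holds as an inconsistency between two stated rules. The tables use different upper-GI levels, stage 0 is undefined, and the one shared level is worded so that absent or non-protracted symptoms can be graded II. The II-IV endpoint and eligibility for further cycles therefore rest on unwritten site practice.

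The direction is known: any error from this source raises the II-IV count, by up to 3.1 points per misgraded patient on 32 evaluable patients. The total is not known; a site that grades by clinical judgement may show no inflation at all. It would be going too far to say that the endpoint is inflated as a matter of fact. The analysis of 6-month OS, the sample size and the grade III-IV stopping rule do not use the I/II boundary. The correction is worth making because that boundary also governs continuation of study treatment.

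**What to change.** Reconcile the staging and grading tables in Appendix II. Upper-GI stage 0 should be defined, the stage descriptions and the grading table should use the same levels, and one unambiguous mapping from upper-GI stage to grade should apply at all sites. Which symptom description belongs to which grade is a clinical decision for the sponsor; this review does not propose one.

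Then re-check every recorded grade II in which the upper-GI stage alone decided the grade, and note in the report of the II-IV endpoint whether any were reclassified. The cost is a correction to one appendix, its circulation to sites, and a review of the existing GVHD forms. No sample size or stopping boundary has to be recalculated.

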### University Of Minnesota Acute GVHD Grading

Acute GVHD Grade	Skin Stage	Liver Stage	Lower GI Stage	Upper GI Stage
I	1-2	0	0	0
II	3	1	1	1
III	-	2-4	2-3	
IV	4	-	4	

- Each column identifies minimum criteria for organ grade.
- Each grade is based on maximum stage for each individual organ involved

e.g. Grade II = skin stage 3 and/or liver stage 1 and/or gut stage 1 and/or UGI stage 1

**Late Acute and Chronic GVHD:**

Late acute and chronic GVHD will be assessed using the National Institutes of Health (NIH) Consensus Criteria.

Patient ID: \_\_\_\_\_

Date of late acute or chronic GVHD diagnosis (mm/dd/yyyy)   /   /

**Onset of chronic GVHD was:**

- Progressive (acute GVHD progressed directly to chronic GVHD)
- Interrupted (acute GVHD resolved, then chronic GVHD developed)
- De novo (acute GVHD never developed)
- Chronic GVHD flare (symptoms reactivated within 30 days of drug tapering or discontinuation)

**Karnofsky Performance status:**

- 100 Normal, no complaints; no evidence of disease
- 90 Able to carry on normal activity, minor signs or symptoms of disease
- 80 Normal activity with effort; some signs or symptoms of disease
- 70 Cares for self; unable to carry on normal activity or do active work
- 60 Requires occasional assistance, but is able to care for most of his/her needs
- 50 Requires considerable assistance and frequent medical care
- 40 Disabled; requires special care and assistance
- 30 Severely disabled; hospitalization is indicated. Death not imminent
- 20 Very Sick, hospitalization necessary, active supportive treatment necessary
- 10 Moribund, fatal processes, progressing rapidly
- 0 Dead

**Diagnosis was based on:**

- Histologic evidence / biopsy proven
- Clinical evidence
- Both
- Unknown

**Overall severity of chronic GVHD**

- Mild
- Moderate
- Severe

**Organ/System Involvement (check if yes)**

- Sclerosis of skin
- Other skin or hair involvement (rash, ulcers, pruritus or itching, dyspigmentation, alopecia, lichenoid skin changes, etc)
- Eyes (xerophthalmia (dry eyes), abnormal Schirmer's test, abnormal slit lamp, corneal erosion / conjunctivitis, etc)
- Mouth (lichenoid changes, mucositis / ulcers, erythema, etc)
- Bronchiolitis obliterans
- Other lung involvement

**Organ/System Involvement (check if yes)**

- Gastrointestinal tract (esophageal involvement, chronic nausea / vomiting, chronic diarrhea, malabsorption, abdominal pain / cramps, etc)

- Liver
- Genitourinary tract (vaginitis / stricture, etc)
- Musculoskeletal (arthritis, contractures, myositis, myasthenia, etc)
- Thrombocytopenia (< 100 x 10^9/L)
- Eosinophilia
- Autoantibodies
- Other hematologic involvement
- Serositis
- Weight loss
- Other organ involvement from chronic GVHD

Specify other organ:

Ref: Jagasia MH, Greinix HT, Arora M. National Institutes of Health Consensus Development Project on Criteria for Clinical Trials in Chronic Graft-versus-Host Disease: The 2014 Diagnosis and Staging Working Group Report. Biol Blood Marrow Transplant. 2015 March; 21(3): 389–401.e1. doi:10.1016/j.bbmt.2014.12.001.
